## Introduction

Amblyopia is described as a limitation of the visual function of one or both eyes with no pathological cause, with a prevalence of about 1–5% of the total world population. This disorder is caused by early abnormal visual experience with a functional imbalance between the two eyes owing to anisometropia, strabismus, congenital cataract and ptosis, resulting in a dramatic loss of visual acuity (VA) in an apparently healthy eye (**Baroncelli, and Maffei, 2011**).

Clinically, amblyopia can be defined as the presence in one or both eyes of a VA of 6/12 or worse, with one or more lines of difference in VA between eyes in unilateral amblyopia which cannot be improved by refractive correction. This condition is an alteration of the visual cortex function which is due to suppression and deprivation of one eye leading to unilateral visual deterioration (**Milla, and Piñero, 2020**).

Optical coherence tomography (OCT) is a noninvasive technique that can reveal morphology of the retinal layers in vivo. OCT determines structural changes in the macula that may be correlated with measures of subjective visual function such as visual acuity and visual field (**Bachmann et al., 2006**). OCT angiography (OCTA) can provide vascular system visualization of the posterior segment in amblyopic eyes (**Lu et al., 2022**).

Visual evoked potentials (VEPs) are a non-invasive technique routinely used in clinical and preclinical practice. VEPs allow to quantify the functional integrity of the visual system from the retina via the optic nerves, optic tracts, to the thalamus, and form projections to the visual cortices (**Marenna et al., 2023**).

In strabismic and anisometropic amblyopia, VEP responses are reduced. VEP may be used as an alternative objective method for diagnosis and monitoring of amblyopia (**Moschos et al., 2010**) .

Passive treatments such as occlusion, optical and/or pharmacological penalization, and Bangerter foils have been demonstrated to be potentially useful treatments for amblyopia. Researches are being done on new pharmacological

options to improve and maintain VA after occlusion treatment in amblyopia (**Milla, and Piñero, 2020**).

Adults with amblyopia cannot be treated because their brains do not have enough plasticity. However, results obtained both in clinical trials and in animal models have challenged this traditional view, unmasking a previously unsuspected potential for promoting recovery after the end of the critical period for visual cortex plasticity. These studies point toward the intracortical inhibitory transmission as a crucial brake for therapeutic rehabilitation and recovery from amblyopia in the adult brain (**Baroncelli, and Maffei, 2011**).

Selective serotonin reuptake inhibitors (SSRIs) increase serotonin activity in the brain. While they are mostly known for their antidepressant properties, they have been shown to improve visual functions in amblyopia and impact cognitive functions ranging from attention to motivation and sensitivity to reward (**Gacoin, and Ben Hamed., 2023**).

### **Aim of Study**

To evaluate possible beneficial effects of fluoxetine on improving and maintaining visual function in amblyopia in different age groups using VA, OCTA and VEP.

## **Patients and Methods**

### **Study design:**

A prospective clinical non-randomized comparative controlled study.

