### **Study population:**

Study participants will be recruited from the ophthalmology outpatient clinics of Minia University Hospitals. Imaging will be performed in the Department of Ophthalmology, Minia University Hospital.

Study will include 75 eyes that will be divided into 3 groups:

**Group A:** normal eyes of age-matched controls.

**Group B:** amblyopic eyes treated with patching.

**Group C:** amblyopic treated with patching and flouxetine.

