### **Inclusion Criteria:**

Patients with unilateral amblyopia > 10 years old.

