## **Outcome Measures**

1. Comparison of VA between 3 groups.
2. Comparison of vessel density (VD) of FAZ, superficial capillary plexus (SCP), deep capillary plexus (DCP) and choriocapillaris (CC) between 3 groups in OCTA.
3. Comparison of FVEP and PVEP between 3 groups:
  - FVEP: latency and amplitude of P2.
  - PVEP: latency and amplitude of P100.

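### Fluoxetine is assigned without randomisation, with no stated allocation rule and nothing to make groups B and C comparable, so a C-B difference cannot be separated from selection into the drug group

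*Protocol*

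**What the plan says.** Under Study design the protocol reads "A prospective clinical non-randomized comparative controlled study". Under Study population it says "Study will include 75 eyes that will be divided into 3 groups": A is "normal eyes of age-matched controls", B is "amblyopic eyes treated with patching" and C is "amblyopic treated with patching and flouxetine". The split of the 75 eyes is not given. Neither section has a rule for placing an amblyopic patient in B or C.

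The Inclusion Criteria are one line: "Patients with unilateral amblyopia > 10 years old". There is no upper age limit, no acuity limit and no restriction by cause. The definition of amblyopia in the Introduction, if applied, would bound only the mild end.

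The Aim of Study is "To evaluate possible beneficial effects of fluoxetine on improving and maintaining visual function in amblyopia in different age groups". The first item under Outcome Measures is "Comparison of VA between 3 groups". Acuity, OCTA and VEP are each scheduled before treatment, at 3 months of therapy and 3 months after withdrawal.

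**The concern.** By their labels, B and C share patching and differ in fluoxetine, so C against B is the comparison that answers the aim. Its credibility depends on the two groups being alike apart from the drug, and the protocol provides nothing to bring that about. The matching term is attached to group A, and the text does not say to whom A is matched.

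The room for imbalance is wide. Patients may be 11 or well into adulthood, with any depth and any cause of amblyopia. The protocol's own background discusses plasticity after the critical period, so it treats age as relevant to response. If younger, milder or more motivated patients tend to receive fluoxetine, C can do better with no drug effect. If the drug goes to the hardest cases, a real effect can be hidden. Later adjustment handles only what was measured. Motivation, for instance, is not listed for measurement.

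**Working it through.** **What can be reproduced.** The protocol gives no effect size, SD or power behind the 75 eyes, so there is no planned figure to reproduce. The calculation below only gives a sense of scale.

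**Inputs.**
- From the protocol: 75 eyes, 3 groups, significance at P < 0.05.
- Assumed: equal split, n = 75/3 = 25 per group; two-sided test; Snellen acuity converted to logMAR with SD 0.2 at each visit; B and C differ at baseline by g; baseline-to-follow-up correlation r; no drug effect. It is also assumed that, given baseline acuity, follow-up acuity does not depend on group. Selection therefore acts only through baseline acuity.

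**Formulas.** Bias is taken in the direction of the baseline gap.
- Follow-up acuity, unadjusted: bias = r·g; SE = 0.2·√(2/25) = 0.0566.
- Change from baseline: bias = (r − 1)·g; SD of change = 0.2·√(2(1 − r)); SE = that SD·√(2/25).
- False-positive rate: two-sided rejection probability of a t-test with 48 df and noncentrality bias/SE (critical value 2.011).

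**Main illustration, g = 0.1 (0.5 SD), r = 0.7.**
- Follow-up acuity: bias = 0.7 × 0.1 = 0.07; noncentrality = 0.07/0.0566 = 1.24; false-positive rate 23%.
- Change: bias = −0.3 × 0.1 = −0.03, in the opposite direction; SD of change = 0.2·√0.6 = 0.155; SE = 0.0438; noncentrality = −0.68; false-positive rate 10%.

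**Range over g and r.**

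| Baseline gap g (logMAR) | r | Follow-up: bias, false-positive rate | Change: bias, false-positive rate |
|---|---|---|---|
| 0.04 (0.2 SD) | 0.5 | 0.020, 6% | −0.020, 6% |
| 0.04 | 0.7 | 0.028, 8% | −0.012, 6% |
| 0.04 | 0.9 | 0.036, 10% | −0.004, 5% |
| 0.10 (0.5 SD) | 0.5 | 0.050, 14% | −0.050, 14% |
| 0.10 | 0.7 | 0.070, 23% | −0.030, 10% |
| 0.10 | 0.9 | 0.090, 34% | −0.010, 7% |
| 0.16 (0.8 SD) | 0.5 | 0.080, 28% | −0.080, 28% |
| 0.16 | 0.7 | 0.112, 49% | −0.048, 19% |
| 0.16 | 0.9 | 0.144, 70% | −0.016, 10% |

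**After baseline adjustment.** In a linear model with baseline acuity as covariate, under the same assumptions, the bias from baseline acuity is 0 and the rate returns to about 5%. The imbalance inflates the variance of the contrast by 1 + d²/4, with d the gap in SD units: at d = 0.5 this is 1 + 0.25/4 = 1.06. The result holds only for the measured covariate. Selection on anything unmeasured stays in the contrast, whatever the analysis.

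**The case against.** The design is openly declared. A non-randomised controlled study is a legitimate way to describe an association, and the aim speaks only of possible benefit. That stands: the declaration is not an error in itself. The weakness is that the aim is about an effect of the drug while nothing is fixed to make B and C comparable.

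A reader might infer that the plan compares raw follow-up acuity and ignores baseline. The documents do not support this. Outcome Measures says only that the groups are compared. It does not specify follow-up values, change or an unadjusted test, and Statistical Analysis names only the software and the significance level. The SAP is not at hand and may specify an adjusted analysis. The 23% is therefore one scenario beside the 10% for change, and neither describes the planned test.

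If A is age-matched to both B and C, some similarity in age between B and C would follow. The text leaves that open, and age matching would not balance depth or cause.

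Randomisation may also not be feasible. The protocol gives no reason for or against it. Recruitment from one hospital's clinics, prospective treatment, written consent and a common visit schedule are compatible with it but do not prove that it can be done. Nor do the documents say that one team treats both groups or that patching is identical in B and C.

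**Conclusion.** The concern holds for allocation. As written, a C-B difference cannot be attributed to fluoxetine, because who receives the drug is left open in a population that is broad in age, severity and cause. A SAP could repair this only in part, by adjusting for measured baseline factors.

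The size is unknown. With a baseline gap of half an SD and r = 0.7, a true null would be rejected about 23% of the time on unadjusted follow-up acuity and about 10% on change. With a gap of 0.2 SD the rates are 6 to 10% and 5 to 6%. The group split, SD, gap and correlation are all assumptions. A reader might take the figures as evidence that B and C will differ, but nothing in the protocol shows that an imbalance exists. It shows only that none is guarded against.

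**What to change.** 1. **Before enrolment, randomise.** Allocate consenting amblyopic patients 1:1 to B or C, with concealed allocation stratified by age. Keep A as an unrandomised reference. The cost is a protocol and consent amendment with ethics review, and possibly slower recruitment if some patients or families decline a chance assignment to the drug. Patients already allocated another way cannot be randomised afterwards.
2. **With or without randomisation, adjust.** Analyse C against B with the baseline value of the outcome and age as covariates. Baseline values of acuity, OCTA and VEP are already scheduled, so this needs no new measurement. Add cause of amblyopia if it is recorded; the protocol does not name it as a recorded item, so it may need a line on the data form.
3. **If randomisation is not possible,** state the rule by which patients enter B or C, say to whom group A is age-matched, and word the conclusion as an association between receiving fluoxetine and outcome. This costs a few sentences and a more limited claim.

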### **Ethical considerations:**

All subjects included in this study will be counseled about the details and the nature of the study and will be required to sign a written consent. Ethical approval will be obtained from the local Ethics Committee of Minia University Faculty of Medicine before commencement of the study. The study will be conducted in Ophthalmology Department, Minia university Hospital, Egypt .

### **Study population:**

Study participants will be recruited from the ophthalmology outpatient clinics of Minia University Hospitals. Imaging will be performed in the Department of Ophthalmology, Minia University Hospital.

Study will include 75 eyes that will be divided into 3 groups:

**Group A:** normal eyes of age-matched controls.

**Group B:** amblyopic eyes treated with patching.

**Group C:** amblyopic treated with patching and flouxetine.

### **Inclusion Criteria:**

Patients with unilateral amblyopia > 10 years old.

### **Exclusion criteria:**

- Ocular pathology: media opacity, uveitis, glaucoma, retinal or optic nerve diseases, and history of ocular trauma.
- Poor fixation.
- Lack of cooperation.
- Any psychological disorder.

### **Ophthalmologic Evaluation:**

All patients will undergo a thorough ocular and systemic history taking, as well as a comprehensive ophthalmic examination before, 3 months after patching and fluoxetine therapy and 3 months after therapy withdrawal, including:

- Measurement of uncorrected and best-corrected Snellen visual acuity .

- Assessment of pupillary reflex.
- Anterior segment slit-lamp examination.
- Intraocular pressure (IOP) measurement using Goldmann applanation tonometry (GAT).
- Fundus examination using both binocular indirect ophthalmoscopy (BIO) and slit-lamp biomicroscopy with a +78 D noncontact lens.

### **Ophthalmic Imaging**

Ophthalmic imaging will be performed for all patients before, 3 months after patching and fluoxetine therapy and 3 months after therapy withdrawal. Spectral-domain OCTA imaging will be done using the Avanti RTVue-XR system (Optovue, Fremont, CA, USA) which utilizes a split-spectrum amplitude-decorrelation angiography (SSADA) algorithm to extract OCTA information.

The machine has a light source centered on 840 nm with a bandwidth of 50 nm. It is capable of an A-scan acquisition rate of 70,000 scans/second allowing for an axial resolution of 5  $\mu$ m and a horizontal resolution of 20  $\mu$ m. Each OCTA volume contains 304 x 304 A-scans. Two consecutive B-scans are obtained at each fixed location before proceeding to the next position .

In order to minimize motion artifacts, 2 orthogonal OCTA volumes are acquired to perform motion correction. The Angio Retina protocol will be used for OCTA image acquisition. Evaluated parameters will include measurement of the foveal avascular zone (FAZ) and vessel density (VD) at the levels of the superficial capillary plexus (SCP) and deep capillary plexus (DCP) of the macula, as well VD of the choriocapillaris.

### **Flash VEP (FVEP) and pattern VEP (PVEP)**

Ophthalmic functional assessment by FVEP and PVEP will be performed for all patients before, 3 months after patching and fluoxetine therapy and 3 months after therapy withdrawal. FVEP and PVEP will be done using the (Roland Consult supercolor Ganzfeld Q450 SC).

## **FVEP Ganzfeld**

Requirement:

- Light-adapted patient (photopic conditions)
- Pupils non dilated
- 3 x EEG-Electrodes at channel 1
- One eye covered with Impedance < 10 kOhm

## **PVEP**

Requirement:

- Distance patient → monitor: 100 cm
- Light-adapted Patient (photopic conditions)
- Patient refraction / correction for 100 cm viewing distance
- 3x EEG-Electrodes at channel 1 One eye covered
- Impedance < 10 kOhm

## **Outcome Measures**

1. Comparison of VA between 3 groups.
2. Comparison of vessel density (VD) of FAZ, superficial capillary plexus (SCP), deep capillary plexus (DCP) and choriocapillaris (CC) between 3 groups in OCTA.
3. Comparison of FVEP and PVEP between 3 groups:
  - FVEP: latency and amplitude of P2.
  - PVEP: latency and amplitude of P100.

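### All three outcomes compare three groups, one of them normal eyes, and none identifies patching plus fluoxetine versus patching alone, the only contrast that answers the aim

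*Protocol*

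**What the plan says.** The Aim of Study section sets the objective as "To evaluate possible beneficial effects of fluoxetine on improving and maintaining visual function in amblyopia". The design is "A prospective clinical non-randomized comparative controlled study".

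Under Study population, "Study will include 75 eyes that will be divided into 3 groups". Group A is "normal eyes of age-matched controls", Group B is "amblyopic eyes treated with patching", and Group C receives patching together with fluoxetine. The split of the 75 eyes between groups is not given.

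The Outcome Measures section lists VA as "Comparison of VA between 3 groups". The OCTA and VEP outcomes are likewise stated as comparisons across the three groups. No outcome singles out a pair of groups, names a visit, or says whether values or changes are compared. The evaluation, imaging and VEP sections schedule measurements before therapy, at 3 months, and 3 months after withdrawal.

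The Statistical Analysis section names the software and a significance threshold of P<0.05. It names no test.

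The Introduction characterises amblyopia clinically by "a VA of 6/12 or worse, with one or more lines of difference in VA between eyes". It adds that VEP responses are reduced in strabismic and anisometropic amblyopia.

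**The concern.** The aim and the outcomes do not ask the same question. Groups B and C, as described, differ only by fluoxetine, so C versus B carries the drug effect. A comparison that also includes Group A mixes that effect with the difference between diseased and healthy eyes, which for VA exists almost by definition.

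Two things are at stake. First, with P<0.05 as the only stated criterion, a significant overall result could be reported as support for fluoxetine when it shows only that amblyopic eyes see less well than normal ones. Second, treatment is not allocated at random, so B and C may differ before therapy. If unadjusted follow-up values were compared, any such difference would pass straight into the apparent treatment effect.

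**Working it through.** The protocol gives no power, effect size or SD, so there is no figure of its own to reproduce. The question is how often an overall three-group test would be significant if fluoxetine did nothing.

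**Inputs**
- Total of 75 eyes in 3 groups (Study population). Assumption: 25 per group.
- Significance level 0.05 (Statistical Analysis).
- Assumption: one-way ANOVA, common SD, since no test is named.
- Fluoxetine effect set to zero, so B and C have the same mean and normal eyes differ from both by d SD.
- Size of d for VA: 6/12 is log10(12/6) = 0.30 logMAR. Assumption: a normal eye is at about 0.0 logMAR. The gap is then at least about 0.30, or 1 to 2 SD if the SD is 0.30 to 0.15 (assumption).

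**Formula**

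With group means (0, d, d), the grand mean is 2d/3. The noncentrality is λ = 25 × [(2d/3)² + (d/3)² + (d/3)²] = 25 × (6/9)d² = 16.67d². The rejection probability is the chance that a noncentral F with 2 and 72 degrees of freedom exceeds the 5% critical value of 3.12.

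**Results, fluoxetine effect zero**

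| Gap d (SD) | λ | P(significant) |
|---|---|---|
| 0 | 0 | 0.05 |
| 0.3 | 1.50 | 0.17 |
| 0.5 | 4.17 | 0.42 |
| 0.8 | 10.67 | 0.82 |
| 1.0 | 16.67 | 0.956 |
| 1.5 | 37.50 | 0.9999 |
| 2.0 | 66.67 | >0.999 |

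**Sensitivity**
- Unequal groups (A/B/C) at d = 1: 0.87 for 15/30/30 and 0.97 for 35/20/20.
- If patching narrows the VA gap to 0.20 logMAR: 0.66 at SD 0.30, 0.96 at SD 0.20.
- If it narrows to 0.10 logMAR: 0.20 at SD 0.30, 0.42 at SD 0.20, 0.96 at SD 0.10.
- Simulation with SD 0.05 in normal and 0.20 in amblyopic eyes: ANOVA and Kruskal-Wallis are both significant in about 100% of trials at a gap of 0.30 or 0.20. At 0.10 the rates are 62% and 68%.

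**Direct contrast**

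In the same simulations, a t test of C against B was significant in 5.0% to 5.3% of trials, whatever the gap to normal eyes. That is the error rate wanted.

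**Other outcomes**

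For VEP the protocol gives a direction but no size. For OCTA it gives neither. No rejection probability can be attached to them from the document; the table shows only how the answer would depend on d.

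**The case against.** The strongest objection is that the protocol commits to no overall test. A comparison across three groups can be carried out as pairwise comparisons, C versus B among them, and the choice of test and covariates is commonly left to an SAP, which is not shown. This stands as far as the test goes: a reader might infer that the trial's stated test is bound to be positive, and the document does not support that. It does not answer the point about the outcomes. Which groups an outcome compares is stated in the protocol, in a form that does not match the aim.

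Four further inferences should be resisted.

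- **Near-certain significance for every outcome.** The calculation supports this only for VA, and only while the gap stays near 0.30 logMAR. Moreover, 6/12 is a definition in the Introduction, whereas the inclusion criterion says only unilateral amblyopia.
- **Follow-up values chosen over change.** The Outcome Measures section is silent on this. Baseline is measured, so either analysis remains open.
- **Loss of power from testing C versus B as one of three pairs.** At 25 per group and a C-B effect of 0.81 SD, Tukey's method would give about 68% power against 80% for a single contrast. No post-hoc method is stated, though, and Fisher's protected procedure keeps 79% to 81% in simulation at gaps of 1 to 2 SD. The loss is hypothetical.
- **A specific precision gain from baseline adjustment.** Any figure needs a baseline/follow-up correlation, which the protocol does not give.

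The design itself does contain the right contrast. The defect lies in how the outcomes are written.

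**Conclusion.** The point holds in this form: all three outcomes are three-group comparisons that include normal eyes, and none identifies C versus B, although only that contrast addresses the aim. An overall three-group test would not estimate the fluoxetine effect. For VA it would be significant in about 96% of trials at a 1 SD gap and over 99.9% at 2 SD with no drug effect, but in only 42% at 0.5 SD and 17% at 0.3 SD. These figures rest on 25 eyes per group, a one-way ANOVA, and an assumed SD and normal acuity, none of which the protocol states. They describe what would follow if an overall test were used, not a test the protocol has fixed.

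The lack of a visit and of baseline adjustment adds to the problem, because in non-randomised groups unadjusted follow-up values would carry any baseline difference between B and C into the result.

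**What to change.** Reword outcomes 1 to 3 so that the treatment comparison is Group C minus Group B in the amblyopic eye, at each post-baseline visit (3 months, and 3 months after withdrawal). Estimate it by ANCOVA or a repeated-measures mixed model, with the baseline value of the same measure and age as covariates, and report the difference with its 95% CI.

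Keep Group A as a normal reference, for example against B and C combined at baseline, outside any test of treatment. State plainly that baseline adjustment does not remove all confounding from non-randomised allocation.

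The cost is wording in the outcome section and the analysis plan. Baseline data are already scheduled, and no further patients or measurements are needed. The change should be made before results are seen, since a contrast chosen afterwards carries less weight.

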## **Statistical Analysis:**

- Results will be analyzed using IBM SPSS.
- P value < 0.05 will be considered significant.

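### No primary outcome or visit is named among nine co-equal outcomes, and the only decision rule is a flat P < 0.05

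*Protocol*

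**What the plan says.** The Outcome Measures section of the protocol gives one numbered list:

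- Visual acuity: "Comparison of VA between 3 groups".
- OCTA: "Comparison of vessel density (VD) of FAZ, superficial capillary plexus (SCP), deep capillary plexus (DCP) and choriocapillaris (CC) between 3 groups in OCTA".
- Flash VEP: "FVEP: latency and amplitude of P2".
- Pattern VEP: "PVEP: latency and amplitude of P100".

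No item is called primary or secondary. The clinical examination, the imaging and the VEP recordings are each scheduled "before, 3 months after patching and fluoxetine therapy and 3 months after therapy withdrawal", which gives a baseline and two later visits. No visit is named as the main one. The Aim of Study does not rank anything either: it speaks of "improving and maintaining visual function in amblyopia in different age groups using VA, OCTA and VEP". The Statistical Analysis section has two lines. One names the software and the other is the threshold, "P value < 0.05 will be considered significant".

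**The concern.** An SAP can supply the test, the model and a multiplicity method. The choice of the outcome and time point that answer the trial's question belongs in the protocol. Here the protocol does address outcomes and the significance rule, and what it fixes is a set of unranked outcomes under a single 0.05 threshold.

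The aim covers both improvement and maintenance, measured three ways. A lower P100 latency at one visit, a higher deep-plexus vessel density at the other, or a better acuity at either could each be presented as the answer. Nothing in the text says which result would count as a negative trial. The 75 eyes are likewise tied to no particular outcome.

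**Working it through.** **The plan's own figure.** The only error-rate figure in the protocol is the per-test threshold of 0.05. It states no overall error rate, power, effect size or standard deviation, so there is nothing further to reproduce. Sidedness is not stated; two-sided tests are assumed below.

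**Count of outcomes (Outcome Measures).** Acuity 1 + OCTA 4 (FAZ, superficial plexus, deep plexus, choriocapillaris) + flash VEP 2 + pattern VEP 2 = 9.

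**Count of visits after baseline (Ophthalmologic Evaluation, Ophthalmic Imaging, VEP section).** 2 for every modality.

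**Relevant contrast (Study population).** Group C (patching and fluoxetine) against Group B (patching) is the only contrast that isolates fluoxetine. This gives 9 tests at one visit, or 9 × 2 = 18 if each visit is tested separately.

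**Independent tests, no fluoxetine effect.** With m tests:

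- At least one false positive in either direction: 1 − 0.95^m.
- At least one favouring fluoxetine: 1 − 0.975^m.
- Expected number in either direction: 0.05 × m.

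| Tests | Expected false positives | At least one, either direction | At least one favouring fluoxetine |
|---|---|---|---|
| 9 | 0.45 | 1 − 0.95^9 = 37.0% | 1 − 0.975^9 = 20.4% |
| 18 | 0.90 | 1 − 0.95^18 = 60.3% | 1 − 0.975^18 = 36.6% |

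**Correlated tests.** The outcomes come from the same eyes, so independence gives the high end of the range. The protocol gives no correlations; those below are assumptions. They were applied to simulated normal test statistics (300,000 to 400,000 draws).

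With one common correlation among all tests, the chance of at least one false positive in either direction is:

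| Correlation | 9 tests | 18 tests |
|---|---|---|
| 0.3 | 33% | 51% |
| 0.5 | 27% | 40% |
| 0.7 | 20% | 28% |

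With separate correlations between outcomes and between visits, for 18 tests in either direction:

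| Between outcomes | Visits 0.5 | Visits 0.7 | Visits 0.9 |
|---|---|---|---|
| 0 | 58% | 55% | 48% |
| 0.3 | 52% | 49% | 43% |
| 0.5 | 44% | 41% | 36% |

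Across the two tables the 18-test risk runs from about 28% to 58%. Even a common correlation of 0.9 among all 18 statistics, an extreme assumption for measures as different as acuity, vessel density and VEP, leaves 15%.

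**The case against.** The strongest reply is that much of this may be settled in an SAP that is not at hand, and that the text does not say what a critic may read into it. Four parts of that reply deserve an answer.

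- **Number of tests.** The visit schedule says when measurements are taken, not that each visit is tested separately. One repeated-measures or omnibus test per outcome is compatible with the text. This stands: 18 is one reading and 9 is another. The nine-test figure of up to 37% does not depend on how the visits are handled.
- **Adjustment.** The threshold sentence does not say that P values are unadjusted; 0.05 could apply to adjusted values. This stands too, so one cannot conclude that the trial will have no multiplicity control. What remains is that the protocol leaves the primary outcome and visit open.
- **Acuity listed first.** First place in a numbered list is not a designation, and the aim names acuity, OCTA and VEP together. The acuity outcome also does not say whether it is uncorrected or best-corrected, though both are measured. The Introduction defines amblyopia as a deficit that refraction does not correct, so best-corrected is the natural reading. This is a small clarification.
- **All three group pairs.** A reader might infer 3 × 18 = 54 tests and 54 × 0.05 = 2.7 expected false positives. The documents do not support this. Thirty-six of those tests involve the normal eyes of Group A. The Introduction defines amblyopia by reduced acuity and says VEP responses are reduced in strabismic and anisometropic amblyopia. Many of those differences are therefore expected to be real, and none of them tests what fluoxetine adds.

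**Conclusion.** The point holds at protocol level: no primary outcome or time point is designated, and the stated rule lets any single result be read as a fluoxetine effect. If fluoxetine has no effect, the chance of at least one false positive for C versus B is up to 37% with nine tests. With 18 tests it is up to about 60% in either direction, or about 37% favouring fluoxetine. Under the assumed positive correlations the 18-test figure is about 28% to 58%.

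A reader might go further and say that a spurious benefit of fluoxetine is likely. The figures do not carry that. The 60% needs 18 separate, independent tests and counts results against fluoxetine as well as for it. In the favourable direction alone the risk stays below one half in every case computed.

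Confidence is high that the primary outcome and visit are missing. It is lower on how many tests will be run. The calculation also takes each test to be valid at 5% on its own; any bias from non-random allocation is a separate matter.

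**What to change.** Name in the protocol one primary outcome at one visit for Group C versus Group B. An example is change from baseline in best-corrected visual acuity (logMAR) of the amblyopic eye, at either the first follow-up visit or the visit after withdrawal. The sponsor has to choose the visit, because the choice decides whether improving or maintaining vision is the primary part of the aim.

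Then:

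- Apply the two-sided P < 0.05 claim to that outcome only.
- Label the other outcomes and the other visit secondary, and report them with estimates and 95% confidence intervals.
- Make any significance claim on a secondary result only after a multiplicity adjustment. Holm is one option, and the details can sit in the SAP.

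This keeps the error rate for the main question at 5%. It needs no new patients, visits or measurements. The cost is that OCTA, VEP and the non-primary visit can no longer carry stand-alone claims.

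The alternative is to keep all outcomes co-equal with a Bonferroni limit of 0.05/9 = 0.0056 for nine tests or 0.05/18 = 0.0028 for 18. That costs power. Assume 25 eyes per group (75/3; the protocol does not state the split), 80% power and a normal approximation. The detectable standardised difference is then (z for the two-sided level + 0.842) × √(2/25). It rises from 0.79 at 0.05 to 1.02 at 0.0056 and 1.08 at 0.0028. One named primary outcome is the cheaper choice.
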